11. SAFETY AND TOLERABILITY ANALYSES

The safety analyses will be run on the Safety population. The analysis of safety in this study will include summaries of the following safety and tolerability data collected for each patient:

- Adverse Events
- Clinical Laboratory Investigations
- C-SSRS
- BDI-II
- Vital Signs
- Physical Examinations and examinations of the oral cavity
- CSFQ-14

11.1 Adverse Events

All AEs, TEAEs, and SAEs will be coded using the MedDRA Dictionary Version 23.0.

The collection of adverse events will begin at the time the patient is consented and screened for the study. Treatment-emergent adverse events (TEAEs) are defined as either new onset AEs with an onset at the time of or following the start of treatment, as indicated by a "no" answer to "Did AE start prior to the first dose?", or a recurrence of an AE (or medical history) present prior to randomization but increasing in severity, frequency or relationship at the time of or following the start of treatment.

An AE summary table will be presented for the following:

- All TEAEs
- TEAEs by severity
- TEAEs leading to study drug discontinuation
- TEAEs by relationship
- SAEs
- Oral cavity TEAEs
- Oral cavity TEAEs by severity

Summaries of incidence rates (frequencies and percentages), of individual AEs by MedDRA SOC and preferred term will be prepared. Such summaries will be displayed for all TEAEs, oral cavity TEAEs, TEAEs by maximum severity, TEAEs by strongest relationship to study drug and post-treatment AEs.

Each patient will be counted only once within each summation level (SOC; preferred term). If a patient experiences more than one TEAE within each summation level, the TEAE with the strongest relationship or the maximum severity, as appropriate, will be included in the summaries of relationship and severity.

In the AE data listings, all AEs will be displayed. AEs that occur prior to randomization will be considered pre-treatment AEs, and will be determined by a "yes" response to the CRF question, "Did the AE start prior to the first dose?" AEs that start on the date of randomization but have a "yes" response to this question will be categorized as pre-treatment AEs. TEAEs will be defined

Protocol: TNX-CY-F307 Page 32 of 45

Final v1.0

from the date of randomization and a "no" response to the CRF question, "Did the AE start prior to the first dose?"

11.1.1 Adverse Events Leading to Discontinuation of Study Drug

A summary of incidence rates (frequencies and percentages) of TEAEs leading to discontinuation of study drug by treatment group, SOC, and preferred term will be prepared for the Safety population.

A data listing of AEs leading to discontinuation of study drug will also be provided, displaying details of the event(s) captured on the CRF.

11.1.2 Serious Adverse Events

A summary of incidence rates (frequencies and percentages) of serious adverse events (SAE) by treatment group, SOC, and preferred term will be prepared for the Safety population. A data listing of SAEs will also be provided, displaying details of the event(s) captured on the CRF.

11.1.3 Oral TEAEs

In light of the study drug's sublingual route of delivery, patients will undergo a detailed examination of the oral cavity at screening and brief examinations at all other visits.

AEs involving the oral cavity may be spontaneously reported by the patient, observed during an oral cavity examination, or both. Oral cavity AEs will be identified by a "yes" response to the CRF question, "Is the AE in the oral cavity?" Additional information will be collected on oral cavity AEs (based on a "yes" response to the above question), including whether the AE occurs immediately or very soon after dosing, an approximation of the duration of the AE (less than or greater than 60 minutes), and whether the AE is still present the next morning upon awakening.

A separate by-patient listing of oral cavity AEs (including pre-treatment oral cavity AEs) will be provided.

11.1.4 **Deaths**

A listing of deaths will also be provided for the Safety Population.

11.2 Clinical Laboratory Evaluations

Laboratory data (analytes for Chemistry and Hematology) will be summarized by treatment and visit for the Safety Population. Descriptive summaries of actual values and changes from baseline will be presented by study visit and last available assessment for each clinical laboratory analyte and each treatment group. 95% confidence intervals will be presented for change from baseline. ET data will be analyzed with the closest visit that does not have a valid assessment value.

Laboratory values will be displayed in the data listings with their corresponding normal ranges, and those values that are outside the normal range will be flagged. For each laboratory analyte, shifts in assessments of abnormality from baseline to each scheduled time point will be presented in shift tables.

A by-patient listing of all clinical laboratory (Chemistry, Hematology and Urinalysis) data will also be provided.

Protocol: TNX-CY-F307 Page 33 of 45

Final v1.0

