before randomization may occur. Therefore, these patients will need to return for an unscheduled visit after the first 2 weeks of washout have been completed. All benzodiazepine drug screening must be sent to the central laboratory for analysis, hence results may be delayed; all other repeat urine drug screening may be conducted on-site. Patients do not have to wait for confirmation of negative centralized benzodiazepine results before starting their 7-day baseline data collection phase, but all results must be confirmed negative prior to randomization.

Patients with a positive screening UDS due to an allowed prescription drug (e.g., headache remedies containing butalbital) do not require further drug screening.

Each clinically significant abnormal laboratory value or other clinically meaningful abnormality should be followed until the abnormality resolves or until a decision is made that it is not likely to resolve. If such abnormalities do not return to normal within a reasonable period, their etiology should be identified and Tonix or designee should be notified. Clinically significant abnormalities in laboratory values after the Screening visit labs will be recorded as AEs.

NOTE: A screening TSH level greater than 1.5 times higher than the upper limit of normal, or ALT or AST level > 2 times the upper limit of normal, is exclusionary; however, the patient may remain in screening to undergo repeat LFT assessments if a transient abnormality (eg, viral illness; effects of a medication being discontinued, etc) is thought to be responsible for their initial elevation.

Table 3: Clinical Laboratory Assessments

Clinical chemistry	Hematology
Alanine aminotransferase (ALT/SGPT) ^a	Hematocrit
Alkaline phosphatase	Hemoglobin
Aspartate aminotransferase (AST/SGOT) ^a	MCH concentration (MCHC)
Bicarbonate	Mean corpuscular hemoglobin (MCH)
Bilirubin (direct and total)	Mean corpuscular volume (MCV)
Blood urea nitrogen (BUN)	Platelet count
Calcium	Red blood cell (RBC) count
Chloride	WBC differential
Cholesterol (total)	Neutrophil count (absolute and %)
Creatine kinase (CK)	Lymphocyte count (absolute and %)
Creatinine	Monocyte count (absolute and %)
Glucose	Eosinophil count (absolute and %)
LDH	Basophil count (absolute and %)
Phosphorus	White blood cell (WBC) count
Potassium	Red blood cell distribution width (RDW)
Protein (albumin and total)	
Sodium	
HbA1c only if glucose > 180 mg/dL	
Thyroid-stimulating hormone (TSH) ^c at	Serum Pregnancy Test at Screening ^b

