13.5. Safety Analyses

Safety analyses will be performed using the Safety Population. The analysis of safety assessments in this study will include summaries of the following safety and tolerability data collected for each patient:

- Incidence of Adverse Events
- Changes from baseline in clinical laboratory tests
- Changes from baseline in vital signs
- Changes from baseline in physical examination findings including examination of the oral cavity
- Monitoring suicidality using the C-SSRS
- Changes from baseline in BDI-II scores

All AEs, treatment-emergent adverse events (TEAE), and serious adverse events (SAE) will be coded using the MedDRA.

An AE summary table will be presented for the following:

- All TEAEs
- TEAEs by severity
- TEAEs leading to study drug discontinuation
- TEAEs by relationship
- SAEs
- Oral cavity TEAEs
- Oral cavity TEAEs by severity

Summaries of incidence rates (frequencies and percentages), of individual AEs by MedDRA SOC and preferred term will be prepared. Such summaries will be displayed for all TEAEs, oral cavity TEAEs, TEAEs by maximum severity, and TEAEs by strongest relationship to study drug.

Each patient will be counted only once within each summation level (SOC; preferred term). If a patient experiences more than one TEAE within each summation level, the TEAE with the strongest relationship or the maximum severity, as appropriate, will be included in the summaries of relationship and severity.

In the AE data listings, all AEs will be displayed.

Laboratory data include analytes for Chemistry and Hematology, and these will be summarized by treatment and visit for the Safety Population. Descriptive summaries of actual values and changes from baseline will be presented by study visit and last on-treatment assessment for each clinical laboratory analyte and each treatment group. 95% confidence intervals will be presented for change from baseline.

Laboratory values will be displayed in the data listings with their corresponding normal ranges, and those values that are outside the normal range will be flagged. For each laboratory analyte, shifts in assessments of abnormality from baseline to each scheduled time point will be presented in shift tables.

A by-patient listing of all clinical laboratory data will also be provided.

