Descriptive summaries (mean, SD, median, minimum, and maximum) of actual values and changes from baseline at each assessment time point and last on-treatment assessment will be calculated for vital signs including weight, BMI, body temperature, pulse rate, systolic blood pressure and diastolic blood pressure. 95% confidence intervals will be presented for change from baseline.

Based on the C-SSRS results, the overall number of patients with lifetime and/or current suicidal ideation (by item and category), suicidal behavior (by item and category), or self-injurious behavior at the screening and baseline visit will be summarized by visit and treatment group. Additionally, the overall number of patients with any suicidal ideation or behavior (by type and in total) or self-injurious behavior while on-treatment will be provided by treatment group. Patients will only be counted once for on-treatment at the worst-case response for each item.

Physical examination data and oral examination data will be presented in data listings.

Descriptive summaries (mean, SD, median, minimum, and maximum) of actual values and changes from baseline at each assessment time point and last on-treatment assessment will be calculated for BDI-II scores. 95% confidence intervals will be presented for change from baseline.

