8.1.2 Data Handling for Patients Who Withdraw/Drop Out from the Study

Patients who withdraw/drop out from the study will have the early termination (ET) data collected at their ET visit included in the analysis at the closest visit (Week 2, 6, 10, 14), using midpoints between visits to window the early termination. If this results in two records for a given visit, then the one closest to the targeted date will be used. Visits beyond day 112 (two weeks past the target day for Week 14) will not be mapped and reported with Week 14; they may appear in the last observation analyses (see below).

For example, a patient with a non-missing Week 10 clinic assessment collected on Day 72 that has early termination data collected on Day 79, would have the early termination data mapped to Week 10; however, since Day 72 data is present and closer to the target date, it would be analyzed and the Day 79 data would be excluded. A patient with missing Week 10 data who early terminates on Day 79 would have the Day 79 data analyzed with the Week 10 data.

Patients who provide 14 weeks of diary pain data will be analyzed as completers for purposes of the primary analysis, even if for some reason they are unable to attend a Week 14 final study visit. As a specific example, a patient who successfully provides 14 weeks of diary data as described in Section 8.2.1, but who is unable to attend a final study visit during the required time window because of travel or other circumstances, would be analyzed as a completer for purposes of the primary endpoint, but would be missing non-diary based secondary outcome measures at the Week 14 endpoint.

For safety data, the last observation available will be summarized in addition to the presentation above (grouping ET visits with the closest planned visit); this will combine the ET visit data with the completers' Week 14 data, regardless of when the ET occurred.

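### The SAP replaces the protocol's last on-treatment value with the last available value for laboratory tests, vital signs and BDI-II without declaring it, and gives two incompatible mapping rules for early-termination BDI-II and vital-sign data

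*SAP*

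**What the plan says.** **Which value is summarised last.** Protocol 13.5 says laboratory summaries "will be presented by study visit and last on-treatment assessment for each clinical laboratory analyte and each treatment group". It uses the same term for the other two measures: "last on-treatment assessment will be calculated for vital signs including weight" and "last on-treatment assessment will be calculated for BDI-II scores". SAP 11.2 reads "Descriptive summaries of actual values and changes from baseline will be presented by study visit and last available assessment", and SAP 11.4 (BDI-II) and 11.5 (vital signs) use the same wording. SAP 8.1.2 agrees with these sections: for safety data it takes the last observation available and pools ET data with completers' Week 14 data whenever the ET occurred. SAP Section 13 lists a single change from the planned analysis, the continuous PGIC analysis.

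**Where ET data go.** SAP 8.1.2 assigns ET data to the closest of Weeks 2, 6, 10 and 14 by midpoint windows. If two records then fall on one visit, it keeps the one nearer the target day. It states that this grouping also applies to safety data. Visits after Day 112 are not reported with Week 14, but "they may appear in the last observation analyses (see below"). SAP 11.2, 11.4 and 11.5 each carry a different rule: "ET data will be analyzed with the closest visit that does not have a valid assessment value". They repeat no Day 112 limit.

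**The concern.** The last-value row is meant to show each patient's status at the end of exposure. Once it may take any later value, measurements made after the drug has been stopped enter it, and a difference between arms can shrink for that reason alone. Safety is the trial's only secondary objective, so a departure from the protocol's safety summary should be deliberate and declared.

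The ET conflict is a separate fault, and it lies within the SAP. A programmer cannot follow both rules. One removes certain dropout values from the by-visit tables. The other places them under a later visit, where they mix with values from patients who stayed on treatment. The BDI-II and vital-sign tables by visit depend on which rule is chosen.

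**Working it through.** **1. Can the last available value differ from the last on-treatment value?** For a completer on schedule it does not: the last dose is on Day 98, Visit 6 is on Day 99, and Visit 7 is a telephone call with no laboratory tests, vital signs or BDI-II scheduled. The documents do open four routes to an off-drug value:

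- Protocol 11.5.2 seeks the ET visit even after a lapse in dosing.
- Protocol 11.5.1 and the notes to Table 2 ask that vital signs and laboratory tests missed at a telephone Week 14/ET visit be collected later, at an unscheduled visit.
- Protocol 12.3.7 requires follow-up of abnormal results: "Each clinically significant abnormal laboratory value or other clinically meaningful abnormality should be followed until the abnormality resolves", or until they are judged unlikely to resolve.
- SAP 8.1.2 lets visits after Day 112 into the last-observation analyses.

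Timing: Day 112 − Day 98 = 14 days after the last planned dose, or 14 × 24 = 336 hours. The label in Protocol Appendix 2 gives a 32-hour elimination half-life for the extended-release capsule. If that carries over to the sublingual tablet (an assumption), 336 / 32 = 10.5 half-lives. Neither document defines on-treatment for these measures in days after the last dose.

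**2. Reproducing the SAP's own ET example.** Inputs are the protocol target days 15, 43, 71 and 99. The midpoints are (15 + 43)/2 = 29, (43 + 71)/2 = 57 and (71 + 99)/2 = 85. For a Week 10 record on Day 72 and an ET visit on Day 79:

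- SAP 8.1.2: 79 < 85, so the ET record maps to Week 10. Its distance from target is 79 − 71 = 8 days, against 72 − 71 = 1 day for the existing record. The ET record is excluded, as the SAP says. With Week 10 missing it becomes the Week 10 value, again as the SAP says.
- SAP 11.4 and 11.5: Weeks 2, 6 and 10 are filled, so the closest empty visit is Week 14. The value is reported there, 99 − 79 = 20 days before target.

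**3. All ET days, BDI-II and vital signs.** Assume each earlier visit was attended on its target day. Take ET Days 2 to 98 without Days 15, 43 and 71: 97 − 3 = 94 days.

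| ET day | SAP 8.1.2 | SAP 11.4 and 11.5 |
|---|---|---|
| 2-14 | Week 2 | Week 2 |
| 16-28 | excluded | Week 6 |
| 29 | midpoint, unresolved | Week 6 |
| 30-42 | Week 6 | Week 6 |
| 44-56 | excluded | Week 10 |
| 57 | midpoint, unresolved | Week 10 |
| 58-70 | Week 10 | Week 10 |
| 72-84 | excluded | Week 14 |
| 85 | midpoint, unresolved | Week 14 |
| 86-98 | Week 14 | Week 14 |

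The rules disagree on 3 × 13 = 39 of the 94 days. The largest displacement is an ET on Day 72 labelled Week 14: 99 − 72 = 27 days.

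**4. Laboratory tests.** Protocol 12.3.7 schedules them only at Screening and Week 14/ET, so no Week 2, 6 or 10 value competes. Both rules then choose the same visit, with 0 of 94 days discordant. They part only after Day 112 (a Day 115 value is unmapped under 8.1.2 and Week 14 under 11.2) or when an unscheduled sample already fills a visit.

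**The case against.** The protocol leaves the full description of analyses to the SAP and gives no on-treatment window, so the SAP may refine the summary. That is fair, but replacing one named summary with another is a change, and Section 13 is where it should appear. It is not a uniform SAP policy either: C-SSRS in SAP 11.3 keeps its on-treatment count.

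A reader might infer that the last-value table replaces on-drug laboratory abnormalities with recovered values and so hides drug effects. The documents do not support that. Follow-up may end with a judgement that the abnormality will not resolve. SAP 8.1.2 describes the last observation as ET data combined with completers' Week 14 data and does not say that repeat samples overwrite them. By-visit summaries, shift tables, out-of-range flags and patient listings remain, and clinically significant laboratory abnormalities after screening are recorded as adverse events.

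A reader might also carry the Day 79 example over to laboratory tests, or hold that the last-value table is the only one containing every early terminator. Neither holds. Scheduled laboratory samples do not conflict at Day 79, and by-visit tables also contain ET values: under 11.2, 11.4 and 11.5 because these go to an empty visit, and under 8.1.2 wherever no nearer record exists.

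Finally, the contradiction could be settled in favour of the rule in 11.2, 11.4 and 11.5, which keeps more ET values in the by-visit tables. That would be consistent, but it labels values with visits the patients did not reach. It cannot be defended on the ground that the specific section overrides the general one, because 8.1.2 expressly includes safety data.

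**Conclusion.** Both parts hold. The move from last on-treatment to last available is an undeclared departure from Protocol 13.5 for laboratory tests, vital signs and BDI-II. It can put off-drug values into the last-value summary and dilute a drug effect there. How often is unknown: the documents give no count of ET visits after a dosing lapse or of late unscheduled collections.

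The ET conflict lies within the SAP and matters in practice for 11.4 and 11.5. The 39 of 94 figure counts calendar days and assumes earlier visits were attended on target with the measure taken; it does not forecast the share of patients affected. A visit held by telephone, for example, leaves vital signs empty and removes the conflict there. The SAP calls Day 112 two weeks past the Week 14 target, which implies Day 98. Moving all targets one day earlier shifts the ranges by one day and makes the 20-day gap 19 days; the pattern is unchanged.

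These are descriptive safety summaries. The primary analysis and alpha are not affected.

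**What to change.** 1. In SAP 11.2, 11.4 and 11.5, restore the last on-treatment summary and state the permitted lag, in days, between last dose and assessment. Align the safety paragraph of 8.1.2 with it.
2. List off-drug values obtained after that lag separately.
3. Delete the ET sentence in 11.2, 11.4 and 11.5, so that the windows and Day 112 limit of 8.1.2 govern all by-visit tables. State which visit receives an ET on a midpoint day (29, 57 or 85).
4. State that an ET value dropped from a by-visit table stays eligible for the last on-treatment row, so that it is not lost from both summaries.

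The cost is SAP wording and one date filter in programming. The downside is slightly fewer values in the last-value and by-visit tables. If the sponsor prefers the last available value, the minimum is to declare the change in Section 13, but off-drug values would still enter the row.

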11.3 Columbia Suicide Severity Rating Scale (C-SSRS)

The C-SSRS is an instrument that measures suicidal ideation and behavior, as represented by the items displayed in the table below. Frequency counts of yes/no responses to each item, and whether any suicidal ideation or behavior is present, will be summarized as described below.

The overall number of patients with lifetime and/or current suicidal ideation (by item and category), suicidal behavior (by item and category), or self-injurious non-suicidal behavior at the screening and baseline visit will be summarized by visit and treatment group.

Additionally, the overall number of patients with any suicidal ideation or behavior (by type and in total) or self-injurious behavior while on-treatment will be provided by treatment group. Patients will only be counted once for on-treatment at the worst-case response for each item.

Category	Items
A) Suicidal Ideation	(1) Wish to be dead
	(2) Non-specific active suicidal thoughts
	(3) Active suicidal ideation with any methods (not plan) without intent
	to act
	(4) Active suicidal ideation with any some intent to act, without
	specific plan
	(5) Active suicidal ideation with specific plan and intent
B) Suicidal	(6) Preparatory acts or behavior
Behavior	(7) Aborted attempt
	(8) Interrupted attempt
	(9) Actual attempt
	10) Completed suicide
	Suicidal Behavior present (composite of items 6-10)
	Non-Suicidal Self-Injurious Behavior

A data listing of C-SSRS results will include only patients with suicidal ideation, suicidal behavior, or self-injurious behavior without suicidal intent at any visit. For patients with suicidal ideation, suicidal behavior, or self-injurious behavior without suicidal intent at any time, data from all visits will be displayed.

